**Figure 3 Blood draw schedule:**

	Screening		Treatment					Follow-up				
Visit no:	-2	-1	1	1b	2	3	3b	4	5	6	7	post
Weeks			0		4	8		9	14	20	52	final
Days			0	1	28	56	57	63	98	140	366	dose
Safety blood samples HbA1c & glucose		11			11			11	11	11	11	
DRB1*0401 and A*02	2											
Serum for Aabs	2											
Serum for insulin cell free DNA	8											
Serum for: Aabs, cystatin-c, insulin cell free DNA, other			10					10	10	10	10	
MMTT			25						25			
Blood to accompany skin biopsies												20
Serum for gold concentrations (morning urine also to be sent)			1	1			1	1	1	1	1	
PBMC's T reg assay, T cells, CD4 & CD8 tetramers, Elispots & biobank storage.			64					64	64*		64	
Flow cytometry			2					2	2		2	
Serum for gold concentration before contact hypersensitivity testing												1
Total	12	11	102	1	11	20	1	88	113	22	113	1

\*in subjects with immune responses of interest visit 4, an additional blood sample up to 70mls (35mls for under 18s) may be requested between visit 4 and visit 6.

Volumes for the study within an 8-week period coincide with guidelines of the National Institute of Health (ie blood collection should be <550ml per 8-week period for adults, and no more than 5ml/kg in a single day and no more than 9.5ml/kg in any 8 week period for under 18's) and are those used by the Type 1 diabetes clinical trial consortium, Type 1 Diabetes Trial Net ([www.diabetestrialnet.org](http://www.diabetestrialnet.org)).

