## **14 SAMPLE SIZE**

The single group study provides 8 patients on active treatment from whom it will be possible to collect safety data. This is considered optimal to achieve sufficient data to inform future study designs and on which to base future sample size calculations.

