3.3. Analysis populations

- Intention to treat population
All patients enrolled in the study
- Per protocol population
Patients receiving all three injections

4. Statistical Principle

The sample has not been powered to detect significant differences before and after treatments. Data will be analysed by simple descriptive statistics.

All patients enrolled will be followed up and included unless they withdrew from the study before the administration of the first dose. An intention to treat analysis will be carried out. Per protocol analyses may also be carried out alongside the intention to treat analysis if necessary.

Adherence to the intervention will be assessed by missed dose (protocol violation) and delayed / missed followup visits (protocol deviation).

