5.1. Analysis of outcomes

5.1.1. Primary outcome

Assessment of the safety of C19-A3 GNP administration in terms of adverse events at the dose used is the primary outcome. This includes general safety concerns, induction of hypersensitivity and exacerbation of β -cell specific autoimmunity with accelerated β -cell loss. All enrolled patients will be included in the following analysis.

General Safety

To address general safety concerns at screening and 0, 4, 8 and 14 weeks a physical examination will be conducted. A review of AEs will be performed at all visits according to seriousness, causality and expectedness. Types of AEs, body systems involved and outcomes of the AE will be categorised and analysed by incidence per person dose used. All AEs will be collated

Hypersensitivity

Patients will be observed for local and systemic reactions post injection. Number of local reactions will be analysed by incidence per person dose used, size of the erythema note and time taken for erythema note size to be reduced to < 1 cm will be analysed by mean and standard deviation. Systemic reactions will be analysed by incidence per person dose used. Therapies used and outcome will be counted and reported.

Exacerbation of β -cell specific autoimmunity with accelerated β -cell loss

Differences between week 0 and 14 will be calculated for each patient and summarised by mean and standard deviations for the following parameters:

- Measurement of islet cell autoantibodies (against insulin, GAD-65, IA-2 and ZnT8)
- Measurement of pro-inflammatory β -cell specific T cell responses (analytes to be defined)

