5.1.2. Secondary outcomes

Differences in the parameters set below will be calculated for each patient and summarised by mean and standard deviations. Potential differences between patients receiving treatment within and outside treatment schedule will also be explored, if required.

- T cell responses to C19-A3 GNP as determined by changes from baseline of interferon gamma and IL-10 ELISPOT responses to this peptide in blood following treatment at weeks 0, 9 and 14.
- T cell responses to C19-A3 GNP as determined by changes from baseline of interferon gamma and IL-10 ELISPOT responses to this peptide in

draining axillary lymph node before treatment and following the last treatment administration (four aspirations: before and after visit 1 and visit 3)

- Changes in additional immunological biomarkers (e.g. flow cytometry profiles, T reg assays, autoantibodies, beta cell and T cell free DNA markers) from baseline at week 0, 9 and 14.
- Effects on residual insulin requirement and c-peptide secretion at week 14 as compared to baseline as assessed by secreted C peptide AUC after a mixed meal tolerance test and a stimulated urine c-peptide test.
- Effects on glycaemic control assessed by blood sugar profiles and HbA1c at week 14 as compared to baseline
- Scores on quality of life and diabetes self-management (week 0 and week 14).

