|--------------|-----------|----------|-------------------|------------|-----------|------|----------------------|
| Screening No | Centre No | Visit No | HbA1c at Visit -1 | Serum Aabs | DRB1*0401 | A*02 | Pregnancy test (Y/N) |
|--------------|-----------|----------|-------------------|------------|-----------|------|----------------------|

Cont'd

| | | | |
|-----------------|--------------------------|----------------------|-----------------------|
| Urine C peptide | Albumin/creatinine ratio | Beta 2 microglobulin | Insulin cell free DNA |
|-----------------|--------------------------|----------------------|-----------------------|

KCL

- Table 4 shows the headings of the data file for assessing adherence to study intervention

| | | | | | | | |
|--------------|-----------|---------------|---------------|---------------|--------------|--------------|--------------|
| Screening No | Centre No | Visit 1 date* | Visit 2 date* | Visit 3 date* | Visit 4 date | Visit 5 date | Visit 6 date |
|--------------|-----------|---------------|---------------|---------------|--------------|--------------|--------------|

*Please flag up withdrawn patients or patients with treatment received date different from the visit date

- Endpoints Analysis (clinical observations)

Table 5 shows the headings of the data file for endpoints assessment with clinical observations

| | | | | | | | | |
|--------------|-----------|----------|-------|--------------|--------------|---------------------|--------------|----|
| Screening No | Centre No | Visit No | Rx No | Sbp (pre-Rx) | Dbp (pre-Rx) | Heart rate (pre-Rx) | T°C (pre-Rx) | Wt |
|--------------|-----------|----------|-------|--------------|--------------|---------------------|--------------|----|

Cont'd

| | | | | | | |
|---------------------|----------------------------------|--|--------------------------|--------------------------------|-----------------------------------|---|
| ECG performed (Y/N) | If N, separate list ¹ | If Y, (normal / abnormal, not sig/ abnormal and sig) | Phy exam performed (Y/N) | If N, list reason ² | If Y, Any system abnormal ? (Y/N) | If abnormal, separate list ³ |
|---------------------|----------------------------------|--|--------------------------|--------------------------------|-----------------------------------|---|

Cont'd

| | | | | | | |

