¹List reason for not performing ECG by subject and visit no in a separate spreadsheet. ²List reasons for not completing physical examination by subject and visit no in a separate spreadsheet. ³List all information about the abnormalities as captured in CRF by patient and visit no in a separate spreadsheet. ⁴List all clinically significant abnormalities as captured in CRF by patient and visit no in a separate spreadsheet. ⁵List changes in insulin as captured in the change of insulin log by patient in a separate spreadsheet. ⁶List concomitant medications as captured in concomitant medication log by patient in a separate spreadsheet. ⁷List reaction details as captured in post injection skin reaction log by patient and visit no in a separate spreadsheet. ⁸List whether the observation was judged to be clinically significant and whether it is an AE.

- Endpoints Analysis (laboratory assays)

Table 6 shows the headings of the data file for endpoints assessment with laboratory assays

For each of the analytes: eg GAD65

| | | | | |
|--------------|-----------|--------------|----------|----------|
| Screening No | Centre No | Treatment No | Visit -2 | Visit -1 |
|--------------|-----------|--------------|----------|----------|

Cont'd

| | | | | | |
|---------|---------|---------|---------|---------|---------|
| Visit 1 | Visit 2 | Visit 3 | Visit 4 | Visit 5 | Visit 6 |
|---------|---------|---------|---------|---------|---------|

For a full list of all the analytes, please refer to the Data Transferral Plan in Section 10 of the Data Management Plan

- Questionnaire Data

Table 7 shows the headings of the data file for endpoints assessment with questionnaire data

At Visit 1

| | | | | | | |
|--------------|-----------|----------|-------|------------|---------------|--------------|
| Screening No | Centre No | Visit No | Rx No | HFS items* | ADDQoL items* | DTSQs items* |
|--------------|-----------|----------|-------|------------|---------------|--------------|

Multiple columns

At Visit 5

| | | | | | | | |
|--------------|-----------|----------|-------|------------|---------------|--------------|--------------|
| Screening No | Centre No | Visit No | Rx No | HFS items* | ADDQoL items* | DTSQs items* | DTSQc items* |
|--------------|-----------|----------|-------|------------|---------------|--------------|--------------|

Multiple columns

- Safety data

Table 8 shows the headings of the data file for AE assessment

| | | | | | | | |

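### SAP 5.1.1 summarises autoantibody change, part of the primary safety outcome, only as a group mean and SD, and no analysis uses the screening values also scheduled before dosing

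*SAP*

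**What the plan says.** The protocol describes a single group with no control; section 14 says: "The single group study provides 8 patients on active treatment from whom it will be possible to collect safety data". SAP section 4 adds: "The sample has not been powered to detect significant differences before and after treatments".

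SAP 5.1.1 places exacerbation of beta-cell autoimmunity within the primary outcome and gives it two parameters: islet autoantibodies (insulin, GAD-65, IA-2, ZnT8) and pro-inflammatory T cell responses. The analysis reads: "Differences between week 0 and 14 will be calculated for each patient and summarised by mean and standard deviations for the following parameters". It gives no criterion for calling a change an exacerbation, no count of patients and no reference for the size of a change.

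SAP 5.1.2 treats cell-free DNA as secondary, among changes in "autoantibodies, beta cell and T cell free DNA markers) from baseline at week 0, 9 and 14". HbA1c is also secondary and is compared with a baseline whose visit is not named.

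Protocol Figure 3 has two rows that apply only to screening visit -2, "Serum for Aabs" and "Serum for insulin cell free DNA". Both analytes appear again in a combined serum row at visit 1, and section 6.17 puts blood draws before dosing. Protocol Table 1 does not mark the visit -2 draws. In the SAP's data-file specifications (Appendix 2), Table 3 lists serum autoantibodies, insulin cell-free DNA and "HbA1c at Visit -1" as baseline data. Table 6, headed "For each of the analytes: eg GAD65", has columns for visits -2, -1 and 1 onwards.

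**The concern.** Exacerbation happens to a patient, not to a group. Protocol 21.3 accordingly lets the data safety monitoring board stop treatment for one subject. A group mean with its SD does not say who rose, by how much, or whether an antibody became newly positive.

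With no control group, nothing in the planned summary shows how far these markers move in the same patients without treatment. A rise could be dismissed as assay noise or over-read as harm. Protocol 12.1.2 speaks of comparing autoantibodies between groups, but there is only one group. A limited within-patient reference is already scheduled, reaches the statistician in the data files, and has no planned use.

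**Working it through.** **1. Are there two pre-dose samples?** Summing protocol Figure 3 columns (ml) against the printed totals:
- Visit -2: 2 + 2 + 8 = 12 (printed 12). It closes only with the autoantibody (2) and cell-free DNA (8) draws.
- Visit 1: 10 + 25 + 1 + 64 + 2 = 102 (printed 102). The 10 is the combined serum row containing both analytes.
- Visits -1, 4, 5 and 6 also close (11, 88, 113, 22). Visit 7 does not as the text was read (88 against 113). The gap of 25 equals one meal-test draw, which Table 1 marks there, and does not affect this point.

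So autoantibodies and cell-free DNA have a pre-dose pair. Blood T cell assays have one pre-dose draw (64 ml at visit 1).

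**2. HbA1c.** Table 1 marks visits -1 and 1, and protocol 10.3 lists week 0. Figure 3 has no HbA1c/safety draw at visit 1: the column closes at 102 without it and would be 113 with it. A pair cannot be assumed.

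**3. What a mean can hide.** One patient at +70%, seven at -10%:
- mean = (70 - 7 x 10)/8 = 0
- SD = sqrt[(70² + 7 x 10²)/7] = sqrt(800) = 28.3 points

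The SD shows spread but not that a single patient produced it.

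**4. How good is the pre-dose reference?** From 8 pairs (7 degrees of freedom), the 95% limits for an SD are sqrt(7/16.01) = 0.66 and sqrt(7/1.69) = 2.04 times the estimate. Protocol Table 1 caps the screening-to-dose interval at 3 months, after which tests other than genotype are repeated. No minimum is stated for this pair of samples.

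**5. Could the reference support a formal comparison?** Assume independent visit errors with equal SD σ (not given in the documents). The half-width of a 95% interval for a mean over 8 patients is 2.365/sqrt(8) = 0.836 SDs of the quantity averaged.
- Week 14 minus week 0: variance 2σ², half-width 0.836 x 1.414 = 1.18σ.
- That change minus the pre-dose change: variance (1 + 4 + 1)σ² = 6σ², half-width 0.836 x 2.449 = 2.05σ, which is 1.73 times wider.
- Both changes contain week 0, with opposite signs, so their correlation is -σ²/(2σ²) = -0.5. A low week 0 value lowers one and raises the other.

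**6. Could patients beyond the pre-dose range be counted?** Assume no drug effect, no drift, and equal, independent, symmetric errors. The 8 pre-dose and 8 on-treatment changes are then exchangeable as sets, because reversing time order and sign swaps them. The largest of the 16 is an on-treatment change with probability 1/2, so at least one patient is flagged half the time per analyte. Over four antibodies, treated as independent, the chance of at least one flag is 1 - 0.5⁴ = 0.94.

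**The case against.** The SAP calculates a difference for every patient and reports an SD, so a spread like that in the example would be visible. Protocol 10.3 also monitors exacerbation through C-peptide, HbA1c, blood sugars and insulin use. The trial is small and declared unpowered. Autoantibodies at entry serve to confirm autoimmune diabetes (protocol 6.1), and protocol 6.18.2.3 describes frozen serum only at weeks 0, 9 and 14. These points limit the size of the concern. They do not answer it: calculating differences is not a plan to show them, and none of the other measures reports a new antibody.

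Four stronger readings are tempting and are not supported:
- **That the SAP discards the only untreated comparison.** Screening values stay in data-file Tables 3 and 6; they are unanalysed, not discarded. Nor are they the only pre-dose repeats: Table 1 marks post-meal C-peptide at visits -1 and 1, and insulin use is recorded from screening (protocol 12.2.2). Screening C-peptide is a poor reference, since entry needs one value above threshold in up to three tests.
- **That HbA1c is clearly paired and analysed from week 0 alone.** Figure 3 contradicts the first part, and the SAP does not name the baseline visit.
- **That the screening values would give the whole primary exacerbation outcome a reference.** They serve one of its two parameters. Cell-free DNA and HbA1c are secondary.
- **That the interval matches the 14 weeks on study.** Three months is a maximum; a short gap shows assay noise but little natural drift.

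**Conclusion.** The concern holds in a limited form. For autoantibodies, a component of the primary safety outcome is reduced to a group mean and SD that can conceal one patient's rise or a newly positive antibody. For autoantibodies and cell-free DNA, scheduled screening values have no planned analysis.

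The gain from using them is modest: up to 8 untreated changes per analyte, mainly showing assay and short-term variation, with an SD known only to within about 0.66 to 2.04 times its estimate. They support side-by-side description, not a test or a threshold count. This rests on Figure 3 being the schedule followed for visit -2. The interval and false-flag figures assume 8 complete patients and the error models stated above.

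**What to change.** 1. In SAP 5.1.1 (autoantibodies) and 5.1.2 (cell-free DNA), list or plot each patient's screening, week 0 and later values. Show the screening-to-week-0 change and its length in days beside the week 0-14 change.
2. In 5.1.1, report the number of patients who become positive for an autoantibody they lacked before dosing, using a positivity cut-off per assay fixed before database lock.
3. State that this is description only, with no count of patients exceeding the range of pre-dose changes.
4. Name the baseline visit for HbA1c. Include HbA1c in the listing only once Table 1 (visits -1 and 1) and Figure 3 (no visit 1 draw) are reconciled.
5. State that blood T cell responses have no pre-dose pair.
6. Assay a patient's samples in one run only if visit -2 serum is stored; the protocol does not currently assure this.
7. Reconcile Table 1 with Figure 3 for the visit -2 autoantibody and cell-free DNA draws.

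The cost is SAP wording, a short listing or figure, and a correction to the visit schedule. No new visit, sample or patient is needed. The drawback is a reference interval that varies between patients and may be much shorter than 14 weeks, so its length must be shown with every change.

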#### **6.18.2.3 Storage of serum for islet autoantibody and cell free DNA studies.**

Blood will be taken at 0, 9 and 14 weeks and spun down for serum which will be aliquoted and frozen at -80C. Sample will be stored for later islet autoantibody and cell free DNA

analysis. Islet autoantibodies to GAD, IA-2 and ZnT8 will be measured in the Diabetes Research Unit Cymru Laboratories, Swansea University and cell free DNA assays (for beta cell and T cell apoptosis) will be performed via the T1D UK Mechanistic Core laboratories.

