### **10.3 Disease exacerbation**

Laboratory tests for exacerbation of  $\beta$ -cell specific autoimmunity are (i) measurement of islet cell autoantibodies (against insulin, GAD-65, IA-2 and ZnT8) at 0 and 14 weeks; and (ii) measurement of pro-inflammatory  $\beta$ -cell specific T cell responses at 0, and 14 weeks. Clinical manifestation of disease exacerbation will be monitored by measurement of secreted C-peptide AUC after MMTT and stimulated urine c-peptide at 0 and 14 weeks ; HbA1c levels (0, 4, 8 and 14 weeks.); and the record of blood sugars and insulin use at each study visit. Disease specific quality of life questionnaires including hypoglycaemia fear (HFS), treatment satisfaction DTSQ and quality of life ADDQoL will be performed at 0 and 14 weeks.

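### The primary safety summary of beta-cell autoimmunity markers uses weeks 0 and 14 only and leaves out the scheduled week 9 sample, taken one week after the last dose

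*SAP*

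**What the plan says.** SAP section 5.1.1 divides the primary safety outcome into general safety, hypersensitivity and exacerbation of beta-cell autoimmunity. For the last it states: "Differences between week 0 and 14 will be calculated for each patient and summarised by mean and standard deviations for the following parameters". Two parameters follow. The first is "Measurement of islet cell autoantibodies (against insulin, GAD-65, IA-2 and ZnT8". The second is pro-inflammatory beta-cell specific T cell responses, marked "analytes to be defined".

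Protocol section 10.3 agrees on timing. Autoantibodies are measured "at 0 and 14 weeks; and (ii) measurement of pro-inflammatory", and the sentence ends with "specific T cell responses at 0, and 14 weeks".

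Other sections use week 9 as well:

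- SAP section 5.1.2 and protocol section 4.4 set the blood interferon-gamma and IL-10 ELISPOT to the C19-A3 peptide at weeks 0, 9 and 14. The SAP list of additional biomarkers includes autoantibodies and ends "beta cell and T cell free DNA markers) from baseline at week 0, 9 and 14".
- Protocol section 6.18.2.3, on serum for autoantibodies and cell free DNA: "Blood will be taken at 0, 9 and 14 weeks and spun down for serum".
- The footnote to protocol Figure 3 treats visit 4 as informative: "in subjects with immune responses of interest visit 4, an additional blood sample" may be requested before visit 6.

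**The concern.** Protocol section 10.1 names exacerbation of beta-cell autoimmunity as one of two major safety parameters in a first-in-man study. The week 9 sample is the scheduled post-treatment blood sample for these markers that lies closest to completion of all three doses. It is the one that the primary summary does not use.

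If a marker rises after dosing and settles before week 14, the primary safety outcome shows little or no change although the trial measured the rise. The week 9 value would then be read, if at all, among the secondary outcomes and not as safety information. For T cell responses to islet peptides other than C19-A3, no listed summary would clearly show it.

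**Working it through.** There is no power or sample size figure to reproduce here. The check is one of dates, schedules and coverage.

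**Distance from the last dose** (protocol Table 1 days: third dose 56, visit 4 on 63, visit 5 on 98)

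- Visit 4: 63 − 56 = 7 days after the last dose.
- Visit 5: 98 − 56 = 42 days; with the window of ±1 week, 35 to 49 days.
- Gap between the two samples: 98 − 63 = 35 days, or 5 weeks.

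**Is the blood drawn at visit 4?** Protocol Table 1 marks both the autoantibody serum and the T cell assays at visits 1, 4, 5 and 7. In Figure 3 the visit 4 entries are safety blood 11, serum including autoantibodies 10, gold 1, T cell and ELISPOT blood 64, and flow cytometry 2. Their sum, 11 + 10 + 1 + 64 + 2 = 88, equals the printed total for that visit, so the column can be relied on.

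**Which summary uses week 9?**

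| Marker | Primary (SAP 5.1.1) | Secondary (SAP 5.1.2) |
|---|---|---|
| Islet autoantibodies | weeks 0, 14 | weeks 0, 9, 14 |
| ELISPOT to C19-A3, blood | weeks 0, 14, if chosen as analyte | weeks 0, 9, 14 |
| T cell responses to other islet peptides | weeks 0, 14, if chosen as analyte | not explicitly listed |

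The third row arises because protocol sections 6.10 and 6.18.2 run the ELISPOT on C19-A3 and on other islet peptides, whereas SAP section 5.1.2 names only C19-A3.

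**Loose ends in the same text**

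- Protocol section 12.1.2 gives weeks 0 and 14 for autoantibodies, against weeks 0, 9 and 14 in sections 4.4 and 6.18.2.3.
- SAP Table 1 appears to mark the autoantibody serum at visits 1, 3 and 5, where protocol Table 1 has visits 1, 4, 5 and 7. A shifted cell in the PDF extraction could explain this, so it needs a check against the source.
- SAP section 5.1.1 lists insulin autoantibodies, but the analysis list in protocol section 6.18.2.3 names only GAD, IA-2 and ZnT8.

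**Why individual values matter.** With 8 patients, a rise of size d in one patient, with no change in the others, moves the mean by d/8. A mean and standard deviation alone can hide a single case at either week.

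**The case against.** The case for leaving the plan alone has substance. The protocol and SAP agree on weeks 0 and 14 for this component. The mixed meal C-peptide test is also at weeks 0 and 14 in protocol section 10.3, so markers and beta-cell function can be read together at week 14. Week 9 autoantibodies and C19-A3 ELISPOT are already summarised in SAP section 5.1.2. All outcomes are analysed together at the end, and the study is descriptive and not powered for change, so no test or error rate turns on the primary or secondary label. Adverse events are reviewed at every visit, and protocol section 10.3 adds repeated HbA1c and glucose and insulin records.

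Most of this stands and narrows the point. It does not cover a rise confined to the laboratory, which need not produce an adverse event or a change in HbA1c. It also does not give the other islet peptides an explicit week 9 summary; the biomarker list in SAP section 5.1.2 is open-ended and could include them, but does not say so. Adding week 9 takes nothing away from the week 14 reading.

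A reader might infer more than the documents support:

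- That a patient with a transient rise would be declared free of exacerbation. SAP section 5.1.1 has no threshold and no yes/no classification, only a mean and standard deviation.
- That every patient's result is understated. Only a rise that resolves by week 14 is affected.
- That the loss can be quantified. With an assumed half-life h in weeks, the share of a week 9 excess left at week 14 is 0.5^(5/h): 3% for h = 1 and 65% for h = 8. The documents give no kinetics, so this range shows only that the answer depends on an unknown.
- That the extra blood sample after visit 4 is a safety action. The footnote speaks of responses of interest and does not say so.
- That the primary and secondary T cell markers are the same. Protocol section 12.1.2 calls interferon-gamma pro-inflammatory, so overlap is likely, but the primary analytes are still undefined.

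**Conclusion.** The point holds in a limited form. The primary summary of the laboratory markers of exacerbation omits a scheduled sample taken 7 days after the last dose and relies on one taken 42 days after it. What can be missed there is a laboratory-only rise that resolves by week 14. For autoantibodies and the C19-A3 ELISPOT it would still be reported, but only as a secondary outcome. For other islet peptides there is no explicitly listed week 9 summary. A sustained rise would show in the week 14 difference, and one with clinical signs could be picked up through adverse event, HbA1c and glucose or insulin review.

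The size of the effect on the results cannot be stated. The conclusion assumes dosing and visits on schedule, and that the week 9 samples are assayed as protocol Table 1, Figure 3 and section 6.18.2 indicate. This is a worthwhile improvement to the safety outcome at almost no cost; it does not undermine the trial's safety assessment as a whole.

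**What to change.** 1. In SAP section 5.1.1 and protocol section 10.3, add the week 9 minus week 0 difference beside the week 14 minus week 0 difference. Apply it to islet autoantibodies and to pro-inflammatory T cell responses to C19-A3 and the other islet peptides. List each patient's values at both weeks, and use both when describing exacerbation.
2. Define the T cell analytes that SAP section 5.1.1 leaves open.
3. Align the autoantibody time points in protocol section 12.1.2, and state whether insulin autoantibodies are assayed on the week 9 serum.
4. Check the autoantibody serum row of SAP Table 1 (apparently visit 3) against protocol Table 1 (visit 4), and correct it if the difference is real.

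The cost is wording in the SAP and in the protocol sections named, plus one further difference per marker in the output. The protocol already schedules the blood, so no visit or draw is added. If insulin autoantibodies or the other islet peptides are not currently assayed at week 9, those assays would be the only extra work. Sample size, power and error rates do not change.

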### **3.4 Sample size and population to be studied**

8 subjects aged 16 to 40 years with a diagnosis of Type 1 diabetes and some residual endogenous insulin (c-peptide) production will be included in the study. The Cardiff site will recruit subjects from the age of 18 years only and the Swedish site will recruit subjects from the age of 16 years, as the PI is an experienced paediatrician. Patients will be required to possess the HLA DRB1\*0401 genotype and residual c-peptide production as evidenced by a stimulated urine c-peptide: creatinine level > 0.2 nmol/mmol or random serum sample level

of > 60 pmol/l. Residual c-peptide production is required to be able to monitor for disease exacerbation (ie unexpectedly rapid loss of insulin c-peptide production).

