### 6.2 Inclusion criteria

1. Clinical diagnosis of type 1 diabetes for > 3 months (dated from the first insulin injection).
2. Commenced on insulin treatment within 1 month of diagnosis.
3. Age 16 to 40 years

4. 2 hour post-meal UCPCR > 0.2 nmol/mmol or random serum sample > 60 pmol/l on at least one occasion (maximum 3 tests on different days)
5. Possession of 0401 allele at the *HLA-DRB1* gene locus
6. The following birth control methods should be used (considered highly effective with a failure rate of less than 1% per year when used consistently and correctly):
  - combined (estrogen and progestogen containing) hormonal contraception associated with inhibition of ovulation:
    - oral
    - intravaginal
    - transdermal
  - progestogen-only hormonal contraception associated with inhibition of ovulation:
    - oral
    - injectable
    - implantable
  - \_intrauterine device (IUD)
  - \_intrauterine hormone-releasing system ( IUS)
  - \_bilateral tubal occlusion
  - \_vasectomised partner (provided that the partner is the sole sexual partner of the trial participant and that medical assessment of azoospermia has been confirmed)
  - Sexual abstinence (defined as refraining from heterosexual intercourse during the duration of the trial)
7. Written and witnessed informed consent to participate.

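### SAP 5.1.1 makes accelerated beta-cell loss part of the primary safety outcome but takes over only the laboratory half of protocol 10.3, so C-peptide change is left outside the safety analysis

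*SAP*

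**What the plan says.** SAP 5.1.1 divides the primary safety outcome into general safety, hypersensitivity and "exacerbation of β -cell specific autoimmunity with accelerated β -cell loss". For the third part, per-patient differences between weeks 0 and 14 are summarised by mean and SD for two parameters: "Measurement of islet cell autoantibodies (against insulin, GAD-65, IA-2 and ZnT8" and "Measurement of pro-inflammatory β -cell specific T cell responses (analytes to be defined".

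C-peptide appears in SAP 5.1.2, among the secondary outcomes: "Effects on residual insulin requirement and c-peptide secretion at week 14 as compared to baseline as assessed by secreted C peptide AUC", together with the stimulated urine test. Blood sugar profiles and HbA1c follow in the same list.

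The protocol treats exacerbation as a safety matter. Section 10.1 names it among the major safety parameters. Section 3.4 explains the entry restriction: "Residual c-peptide production is required to be able to monitor for disease exacerbation (ie unexpectedly rapid loss of insulin c-peptide production". Section 10.3 first gives laboratory tests (the same autoantibodies and T cell responses) and then the clinical side: "Clinical manifestation of disease exacerbation will be monitored by measurement of secreted C-peptide AUC after MMTT and stimulated urine c-peptide", followed by HbA1c and the record of blood sugars and insulin use.

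**The concern.** The title of the third part of the primary outcome promises something about beta-cell loss, but neither listed parameter measures beta-cell function, and one of the two is not yet specified. The measures that would speak to function are placed where they read as effects of treatment; protocol section 12 likewise presents them as possible beneficial trends.

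At stake is the safety statement of a first-in-man trial. A report that follows SAP 5.1.1 and 5.3 could describe exacerbation without mentioning C-peptide. The entry restriction that protocol 3.4 justifies by monitoring for exacerbation would then feed no safety analysis. Because the planned summary is a mean and SD over about 8 patients, one patient's rapid loss could also go unremarked.

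**Working it through.** The plan states no figure to reproduce: N = 8 is given without a calculation, and SAP section 4 says that the sample is not powered. The check is a comparison of texts, with short arithmetic on what a mean of 8 can show.

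**1. Protocol 10.3 against SAP 5.1.1**

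| Protocol 10.3 | In SAP 5.1.1? | In SAP 5.1.2? |
|---|---|---|
| Islet autoantibodies | yes | yes |
| Pro-inflammatory T cell responses | yes, analytes undefined | IFN-γ ELISPOT |
| MMTT C-peptide AUC | no | yes |
| Stimulated urine C-peptide | no | yes |
| HbA1c | no | yes |
| Blood sugars | no | yes |
| Insulin use | no | yes |

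The laboratory half carries over 2 of 2; the clinical half 0 of 5.

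**2. Where the SAP locates safety.** SAP 4.2 says the safety analysis is that of 5.1.1 and 5.3, and sends metabolic outcomes to 5.1.2. Sections 5.3.1 to 5.3.4 cover blood tests, urinalysis, gold and pregnancy; none lists C-peptide. HbA1c and glucose appear in the safety data file (Appendix 2, Table 9), but only as normal yes/no flags, not as change from baseline.

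**3. What a mean of 8 can hide.** Suppose one patient loses a fraction L of baseline C-peptide and seven do not change. The mean fall is L/8 and the SD is L/√8. With L = 50% (an illustrative value), the mean fall is 50/8 = 6.25% and the SD is 50/2.828 = 17.7%. The SD hints at an outlier but does not show who it is, how long that patient has had diabetes, or whether HbA1c and insulin dose moved too. The 95% half-width of a mean paired change is t(0.975, 7)/√8 = 2.365/2.828 = 0.84 SD.

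**4. Is there a reference for accelerated?** The trial is a single uncontrolled group. Protocol 3.2 and the SAP introduction both accept that beta-cell function may decline or be lost over a few years. Entry is open at any duration beyond "Clinical diagnosis of type 1 diabetes for > 3 months (dated from the first insulin injection". No expected rate and no threshold for unexpectedly rapid loss is given. Purely as an illustration, assume a natural yearly fall a of 20% to 50%. The fall over 14 weeks is 1 − (1 − a)^(14/52):

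- a = 20%: 1 − 0.80^0.269 = 5.8%
- a = 50%: 1 − 0.50^0.269 = 17.0%

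Under that assumption, a mean fall of about 6% to 17% needs no drug effect. The 6.25% in step 3 lies inside this range.

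**5. Antibody panel.** Protocol 6.7, protocol 10.3 and SAP 5.1.1 include antibodies against insulin. For stored serum, protocol 6.18.2.3 says "Islet autoantibodies to GAD, IA-2 and ZnT8 will be measured in the Diabetes Research Unit Cymru Laboratories" and does not list insulin. The passages differ, and nothing in them says which panel is final.

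**The case against.** The strongest reply is that this is a matter of placement. SAP 5.1.2 analyses C-peptide AUC, urine C-peptide, insulin requirement, blood sugars and HbA1c at week 14 with the same per-patient difference, mean and SD. It also covers beta-cell free DNA, which protocol 12.1.2 treats as a marker of beta-cell death. All outcomes are analysed together at the end (SAP 2.3). With a descriptive plan and no error rate to protect, the primary or secondary label changes no test. Protocol 4.3 defines the primary endpoint by adverse events and protocol 4.4 makes C-peptide secondary, so the SAP follows the protocol. All of this stands. It rules out the reading that C-peptide loss would go unanalysed, and it is why the fix should leave the endpoints of protocol 4.4 where they are. It does not answer why the SAP's safety sections name beta-cell loss and neither list nor cross-refer to its measures.

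Two further inferences are tempting and not supported:

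- *That the protocol defines exacerbation only as C-peptide loss.* Section 3.4 glosses it that way in a parenthesis, but section 10.3 also names these same autoantibodies and T cell responses as its laboratory tests. The SAP line reproduces that faithfully.
- *That anti-insulin antibody tells nothing because every participant injects insulin.* The documents establish the exposure, but not that it makes a within-patient change uninterpretable. Three places list the assay.

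It may also be said that no uncontrolled study of this size can show acceleration, so adding C-peptide would not show it either. That is correct, and it is the reason for changing the wording of the conclusion as well as the list.

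**Conclusion.** The point holds as a gap between the SAP's safety analysis and protocol 10.3. None of the five clinical measures of exacerbation is in the SAP 5.1.1 list, and C-peptide is in neither 5.1.1 nor 5.3, while the entry criterion in protocol 3.4 exists to make that monitoring possible. The data and a group summary are already planned in 5.1.2. What is missing is the link to the safety conclusion and the per-patient view.

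The finding rests on the text alone. The 6% to 17% range depends on an assumed yearly fall of 20% to 50% and measures no defect in the SAP; it only shows why a mean fall should not be called accelerated without a reference rate. A finding of no rapid loss would also be weak evidence: 0 of 8 patients has an exact two-sided 95% upper limit of 1 − 0.025^(1/8) = 36.9%.

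**What to change.** 1. In SAP 5.1.1 or 5.3, as a safety assessment that leaves the secondary endpoints of protocol 4.4 in place, add each patient's week 0 to week 14 change in MMTT C-peptide AUC and urine C-peptide ratio (as percent of baseline, with the two raw values), together with HbA1c and insulin dose. List patients individually beside age and diabetes duration, and keep the mean and SD.
2. State how the week 14 insulin dose is derived. SAP Table 1 schedules the record at that visit, but the 7-day average in protocol 12.2.2 names only weeks 0, 4 and 8.
3. Report the result as change in beta-cell function, not as accelerated loss shown or excluded.
4. Define the T cell analytes left open in 5.1.1 before database lock.
5. Reconcile the autoantibody panel between protocol 6.7, protocol 10.3 and SAP 5.1.1 (insulin included) and protocol 6.18.2.3 (insulin not listed), without presuming that insulin should come out.

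Cost: SAP wording, one listing and a panel clarification. MMTT and urine C-peptide are already scheduled at weeks 0 and 14, so no visit, sample or patient is added. The downside is that the trial gives up any claim to show or exclude acceleration, which the design could not support in any case.
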